7.1 Efficacy Assessments

Disease assessments will occur every other cycle for the first 2 evaluations (6 weeks [end of Cycle 2 \pm 1 week] and 12 weeks [end of Cycle 4 \pm 1 week]), and every third cycle (every 9 weeks [e.g., end of Cycles 7, 10, 13, etc., \pm 1 week]) thereafter until progression or more frequently, if clinically indicated. Assessments may be performed within \pm 1 week of the required timepoint and response assessment must be available prior to initiation of dosing at the subsequent cycle.

In case of dose delays, disease assessment should be maintained at the frequencies defined above and response assessment is required prior to resumption of ADCT-301 dosing (only if the interval from last scan is \geq 6/9 weeks, as applicable) to rule out disease progression.

Tumor response will be determined by the Investigator, based on the 2014 Lugano Classification Criteria ([Appendix 13.2](#)) and Global Response Score Grading Scales for CTCL ([Appendix 13.3](#)). Images will be obtained according to local site imaging requirements. Images will be required to be submitted for a central/independent review for Part 2. Submission instructions for the central/independent review will be provided in a separate manual.

7.2 Pharmacokinetic and Pharmacodynamic Assessments

Blood samples (5 mL draw) will be collected for PK assessment processed according to the instructions provided by the bioanalytical laboratory to the clinical sites. The concentration versus time profile of total antibody HuMax-TAC, PBD-conjugated HuMax-TAC and free warhead SG3199 in serum will be determined centrally in Cycles 1 and 2.

In Cycles 1 and 2, whole blood samples for analysis of PK parameters will be collected at the following times: before the start of the ADCT-301 infusion, end of the infusion, and at 1, 3, 6, 24, 48, 96, 168 (Day 8), and 336 hours (Day 15) after the end of the ADCT-301 infusion ([Appendix 13.1.2](#)). In all subsequent cycles, PK blood samples will be collected before the start of the ADCT-301 infusion, at end of the infusion, at End of Treatment (EOT), and 12 weeks following the last ADCT-301 infusion. Additional PK/biomarker blood samples will be collected, at the discretion of the Investigator, during any visit where toxicity is observed. All PK samples will be evaluable as long as the actual collection times are recorded.

Please see [Appendix 13.1.2](#) for details on timing windows for blood sample collection for all PK and pharmacodynamic assessments.

Antidrug (ADCT-301) antibodies will be measured centrally at the following times in serum: before the start of each ADCT-301 infusion, at EOT, at 12 weeks following the last ADCT-301 infusion, and optionally in PK samples if needed.

[REDACTED]

- [REDACTED]
- [REDACTED]
- [REDACTED]
- [REDACTED]
- [REDACTED]
- [REDACTED]

7.3 Safety and Tolerability Assessments

Safety will be assessed based on AEs, SAEs, treatment discontinuations due to AEs, DLTs, hematology, biochemistry, coagulation panel, pregnancy testing (for women of child-bearing potential) and urinalysis test results. Adverse events will be graded according to CTCAE Version 4.0. Additional safety assessments include periodic 12-lead ECG recordings, physical examination, vital sign measurements, and ECOG performance status. A schedule of all assessments, including safety, is provided in [Appendix 13.1.1](#).

7.3.1 Dose-Limiting Toxicities and Dose-Escalation Scheme

7.3.1.1 Definition of Dose-Limiting Toxicities

A DLT is defined as any of the following events, except those that are clearly due to underlying disease or extraneous causes:

- A hematologic DLT is defined as (not applicable for ATLL patients):
 - Grade 3 or 4 febrile neutropenia or neutropenic infection.
 - Grade 4 neutropenia lasting > 7 days.
 - Grade 4 thrombocytopenia.
 - Grade 3 thrombocytopenia with clinically significant bleeding, or Grade 3 thrombocytopenia requiring a platelet transfusion.
 - Grade 4 anemia.
- For ATLL patients, a hematologic DLT is defined as:
 - Any Grade 4 neutropenia lasting \geq 42 days from the start of the cycle in the absence of evidence of residual leukemia.
 - Grade 3 or higher event of thrombocytopenia or a Grade 4 anemia, with a hypocellular bone marrow lasting for \geq 42 days from the start of the cycle, in the absence of evidence of residual leukemia (i.e., with <5% malignant cells).
- A non-hematologic DLT is defined as:
 - Grade 4 tumor lysis syndrome (Grade 3 TLS will not constitute DLT unless it leads to irreversible end-organ damage).
 - Grade 3 or higher (including nausea, vomiting, diarrhea, and electrolyte imbalances lasting \geq 48 hours despite optimal therapy [excluding all grades of alopecia]).
 - Grade 3 or higher hypersensitivity reaction (regardless of premedication) ([Appendix 13.4](#)).
 - Skin ulceration \geq Grade 2.
 - Peripheral sensory or motor neuropathy \geq Grade 2.

Note: The DLT period for dose escalation will be 1 cycle; however, the adaptive dose-escalation algorithm will incorporate cumulative DLTs occurring through Cycle 3.

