5.2.3 Patient Replacements

Patients in Part 1 who discontinue treatment for any reason without a DLT AE before completion of the first treatment cycle will be replaced. No other patients will be replaced.

6 Study Treatments

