7.3.2.3 Reporting Adverse Events

All AEs reported or observed during the study will be recorded on the AE page of the eCRF. Information to be collected includes drug treatment, dose, event terminology, date of onset, CTCAE Version 4.0 assessment of severity and relationship to study drug, date of resolution of the event, seriousness, any required treatment or evaluations, and outcome. With the exception of disease progression, AEs resulting from concurrent illnesses, reactions to concurrent illnesses, and reactions to concurrent medications also must be reported. All AEs will be followed to adequate resolution. CTCAE Version 4.0 will be used to grade all AEs. The CTCAE includes 5 grades (1 to 5), with Grade 5 being death.

Any AE that meets SAE criteria ([Section 7.3.2.1](#)) must be reported to the contract research organization (CRO) immediately (i.e., within 24 hours after the time site personnel first learn about the event). The following contact information is to be used for SAE reporting:

[REDACTED]

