8.4 Analysis Sets

Five analysis sets will be used in this study:

- The Safety analysis set consists of all patients who receive study drug
- The DLT-evaluable analysis set consists of all patients in Part 1 who receive study drug and excludes patients who discontinue from the study during the first 21-day cycle without experiencing a DLT.
- The Efficacy analysis set will consist of all patients with valid baseline data who receive at least 2 doses of study drug or who have documented progression of disease at any time after the first dose of study drug. Patients who do not have a post baseline assessment due to early clinical progression, toxicity, or death will also be included.
- The PK analysis set consists of all patients who receive study drug and have sufficient concentration data for PK analysis.

- The pharmacodynamic analysis set consists of all patients who receive study drug and have sufficient concentration data for pharmacodynamic analysis.

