13.5.3.2 Assignment of Dose Level

The dose-toxicity model will be used to assign patients to doses. However, assignment of dose level is also governed by rules that govern the speed of dose escalation and rules that determine if untried dose levels may be skipped.

There must be complete DLT information through the first cycle (3 weeks) on at least 2 patients in order to escalate. When the dose is escalated, the dose level may increase by 100% as long as no toxicity events are observed. Once a non-DLT toxicity is observed, the dose may only be increased by 67%; and once a DLT is observed, the dose may only increase by 50%. In addition, the dose may never increase by more than 100% or by more than an absolute value of 1) 0.02 mg/kg at dose levels below 0.10 or 2) 0.10 mg/kg for dose levels between 0.10 and 0.30.

The increase in dose level is always constrained by the dose-toxicity model. The dose may never escalate to a dose that is considered unsafe.

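### For non-ATLL patients, a death from febrile neutropenia or anemia recorded only as Grade 5 is, as written, not a DLT, so before the end of Cycle 1 it is replaceable and not DLT-evaluable

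*Protocol*

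**What the plan says.** Protocol 7.3.1.1 lists hematologic DLTs for patients without ATLL. Two of the lines are "Grade 3 or 4 febrile neutropenia or neutropenic infection" and "Grade 4 anemia". No other hematologic line for these patients reaches Grade 5. Among the non-hematologic lines are "Grade 4 tumor lysis syndrome (Grade 3 TLS will not constitute DLT unless it leads to irreversible end-organ damage" and a general line that opens "Grade 3 or higher (including nausea, vomiting, diarrhea, and electrolyte imbalances"; the noun that should follow the grade is missing. The synopsis has the same wording. Section 7.3.2.3 states: "The CTCAE includes 5 grades (1 to 5), with Grade 5 being death".

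DLT status then drives several rules:
- Protocol 5.2.3, replacement: "Patients in Part 1 who discontinue treatment for any reason without a DLT AE before completion of the first treatment cycle will be replaced".
- Protocol 8.4, DLT-evaluable set: it "excludes patients who discontinue from the study during the first 21-day cycle without experiencing a DLT".
- Protocol 13.5.3.2, step size: "once a DLT is observed, the dose may only increase by 50" per cent. After a non-DLT toxicity the limit is 67%.
- SAP 4.1.2 keeps early discontinuers who have completed DLT information, without defining that term. SAP 4.8.1 builds the DLT table on that set.

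**The concern.** The febrile neutropenia line covers Grades 3 and 4, and the anemia line covers Grade 4 only. Elsewhere in the same list, hypersensitivity, skin ulceration, neuropathy and ATLL thrombocytopenia have open upper ends. A reader applying the text literally therefore has no basis for adding Grade 5 to the two closed lines, and there is no separate line for treatment-related death.

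Section 5.2.1 names death among the reasons for leaving treatment. A patient who dies in Cycle 1 of febrile neutropenia or anemia, with the event graded only as 5, has therefore discontinued without a DLT. At stake is whether such a death reaches the data behind the MTD, which is a primary objective.

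**Working it through.** **1. Which fatal events fall outside the list (non-ATLL)**

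| Event recorded only as Grade 5 | Specific line | Could the open non-hematologic line catch it? | Status as written |
|---|---|---|---|
| Febrile neutropenia | Grades 3 and 4 | No, if classed as hematologic | Not a DLT |
| Anemia | Grade 4 | No | Not a DLT |
| Neutropenic infection | Grades 3 and 4 | Arguably, as an infection | Unclear |
| Tumor lysis syndrome | Grade 4; Grade 3 only with irreversible organ damage | Yes on a plain reading, since only Grade 3 is carved out | Unclear |

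**2. Step caps (Protocol 13.5.1 and 13.5.3.2)**

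The stated grid reproduces: 18 levels (0.003 to 0.020 by 0.001) + 6 (0.025 to 0.050 by 0.005) + 5 (0.06 to 0.10 by 0.01) + 4 (0.15 to 0.30 by 0.05) = 33. Escalation is possible from 32 of them.

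The next permitted dose from level d is the highest grid level not above min{d × (1 + cap), d + A, 2d}. A is 0.02 mg/kg below 0.10 mg/kg and 0.10 mg/kg from there up. The comparison is between the 67% cap (death counted as a non-DLT toxicity) and the 50% cap (death counted as a DLT).

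| From (mg/kg) | 67% cap | 50% cap |
|---|---|---|
| 0.006 | 0.01002 → 0.010 | 0.009 → 0.009 |
| 0.015 | 0.02505 → 0.025 | 0.0225 → 0.020 |
| 0.030 | 0.0501, limited to 0.050 → 0.050 | 0.045 → 0.045 |
| 0.045 | limited to 0.065 → 0.06 | limited to 0.065 → 0.06 |
| 0.15 | 0.2505, limited to 0.25 → 0.25 | 0.225 → 0.20 |

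Over the whole grid the two caps differ at 17 of 32 levels: 0.003, 0.005 to 0.013 (nine levels), 0.015, 0.016, 0.018, 0.019, 0.025, 0.030 and 0.15 mg/kg. They agree at every level from 0.035 to 0.10 mg/kg, because the absolute limit binds or the grid rounds to the same dose.

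**3. Effect on the dose model (illustration only)**

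The model is the one in Protocol 13.5.2: logit of the DLT rate = α + βd, with α ~ N(−3, 6²), β ~ N(8, 20²) and the three pseudo-observations (0% at 0.003, 30% at 0.10, 60% at 0.20 mg/kg). A dose is safe if Pr(DLT rate < 30%) exceeds 60%. Assumptions: d is in mg/kg, which the protocol does not state; only the DLT part of the model is used; and the patient sequence is 0/2 at 0.003, 0/2 at 0.006, 0/2 at 0.012, 0/3 at 0.02 and 0/4 at 0.03, followed by one death at 0.045 mg/kg.

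| Death handled as | Pr at 0.15 mg/kg | Highest model-safe dose |
|---|---|---|
| DLT, 1/4 | 0.42 (0.75 at 0.10) | 0.10 mg/kg |
| Dropped, 0/3 | 0.67 | 0.15 mg/kg |
| Dropped and replaced by a DLT-free patient, 0/4 | 0.68 | 0.15 mg/kg |

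The next level from 0.045 is 0.06 mg/kg under either cap, and both posteriors accept it: even at 0.07 mg/kg the probabilities are 0.93 (1/4) and 0.99 (0/3). The example moves the model's ceiling but does not change the next dose.

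A second run kept the Grade 2 part of the model: two clean patients at each of 0.003, 0.006, 0.012 and 0.02, then three at 0.03 with one death. The mean DLT rate at 0.03 mg/kg is 6.7% if the death is a DLT, 2.4% if it is a non-DLT toxicity, and 1.6% if the patient is replaced by a clean one. The highest model-safe doses are 0.10, 0.15 and 0.15 mg/kg.

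**The case against.** The strongest reply is that this is loose drafting. If Grade 3 or 4 is a DLT, nobody would read a fatal case of the same event as something less. Section 7.3.1.2 gives the steering committee the determination of DLTs and lets its medical judgment override the model in the cautious direction. Section 6.5 pauses the study for one Grade 5 event that is not attributable to the disease and is possibly drug-related, within 30 days of the last dose. Section 7.3.2.4 asks for changes in severity to be documented, so a case recorded at Grade 3 or 4 before death has already met the febrile neutropenia criterion (for anemia, Grade 4).

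Much of this stands. It limits the gap to events graded only as 5 and makes a bad dosing decision unlikely. But a pause adds no observation to the model, and a committee override changes neither the replacement rule nor the definition of the DLT-evaluable set. Relying on either means relying on people to depart from the text.

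A reader might go further in three ways that the documents do not support:
- **That the closed ranges are deliberate.** Nothing in the text shows intent.
- **That fatal tumor lysis and fatal neutropenic infection are equally clear gaps.** The criteria are alternatives and the open non-hematologic line may cover both. No stated rule lets the tumor lysis line override it.
- **That the death always disappears.** Section 13.5.1 counts Grade 2 or higher events as non-DLT toxicities, so it could enter the model in that category. Section 13.5.2 says only Grade 2, which leaves its category undefined.

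**Conclusion.** The point holds for febrile neutropenia and anemia in non-ATLL patients, when the event is recorded only as Grade 5. As written, such a death is not a DLT. Replacement and loss of evaluability follow only if it occurs before Cycle 1 is complete. The lost 50% cap matters only if no earlier DLT has been seen, and then at 17 of 32 levels if the 67% cap applies instead.

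The shift in the model-safe ceiling from 0.10 to 0.15 mg/kg depends on the assumed dose scale and patient sequence. It is an illustration, not a forecast. A reader might infer that the MTD will be biased upward; no operating characteristics support that for so rare an event. What is shown is a rule that gives the wrong result in a plausible case, feeds a primary objective, and can be corrected with a few words.

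**What to change.** Reconcile Protocol 7.3.1.1 and the synopsis with 7.3.2.3, 5.2.3, 8.4, 13.5.1, 13.5.2, 13.5.3.2 and SAP 4.1.2, so that:
- the closed grade ranges no longer leave out Grade 5;
- the DLT status of a Grade 5 event in the DLT period, not clearly due to underlying disease or extraneous causes, is explicit;
- that patient's replacement, DLT-evaluability and model category follow from that status, with the two descriptions of a non-DLT toxicity in 13.5.1 and 13.5.2 made to agree;
- completed DLT information in SAP 4.1.2 is defined;
- the missing noun in the open non-hematologic line is restored, which would also help to settle fatal tumor lysis and neutropenic infection.

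The cost is a few words in each place. No new data, visits or patients are needed.

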13.5 Appendix: Dose Escalation Scheme Report

13.5.1 Overview

A primary objective of the dose escalation portion of the study is to estimate an MTD. The MTD will be the highest safe dose that has at least a 60% probability that the dose limiting toxicity (DLT) rate is < 30%. The DLT observation period is 1 cycle.

Dose escalation will begin with the 3 µg/kg starting dose (Dose Level 1). There will be 33 dose levels including all dose levels from:

- 0.003 to 0.02 mg/kg in increments of 0.001
- 0.02 to 0.05 mg/kg in increments of 0.005
- 0.05 to 0.10 mg/kg in increments of 0.01
- 0.10 to 0.30 mg/kg in increments of 0.05

Dose escalation will be conducted according to a continual reassessment method (CRM). Non-DLT toxicity events (i.e. Grade 2 or higher toxicities) will inform the probability of DLT at each dose level. Dose escalation is also conducted according to a set of rules that govern entry into the study and assignment of dose level. These rules allow that untried dose levels may be skipped. The trial is continuously monitored for safety and early stopping for successfully identifying the MTD.

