13.5.2 Continual Reassessment Method

Dose escalation in this study will be conducted using the CRM. For each dose, $d = 1, \dots, 33$, we model the ordinal outcome of no toxicity event, non-DLT (i.e. Grade 2) toxicity event, or a DLT.

We model the log odds of a DLT,

$$\theta_d = \log\left(\frac{\pi_{DLT}}{1 - \pi_{DLT}}\right)$$

with a two-parameter model

$$\theta_d = \alpha + \beta d$$

We model the log odd-odds of a non-DLT toxicity

$$\rho_d = \log\left(\frac{\pi_{grade2}}{1 - \pi_{grade2}}\right)$$

as related to DLTs by including an additive term, γ , which must be > 0 ,

$$\rho_d = (\alpha + \gamma) + \beta d.$$

We place the following independent prior distributions on the parameters.

$$\alpha \sim N(-3, 6^2)$$

$$\beta \sim N(8, 20^2)$$

$$\gamma \sim N^+(3, 6^2)$$

This parameterization imposes that Grade 2 or higher toxicities (which include DLTs) will occur more frequently than DLTs. We use “pseudo-prior” weighting to impose a prior expectation of the rate of DLTs that helps shape the correlation of the parameters. We assume one observation each of three doses. We place one observation with 0% DLT on the 0.003 mg/kg dose, with 30% DLT on the on the 0.10 mg/kg dose, and with 60% DLT on the 0.20 mg/kg dose.

After each patient is treated and assessed for non-DLT toxicity or DLT, the distributions of all parameters are updated and the MTD is estimated based on the posterior probability of DLT at each dose.

Additionally, we define a dose as safe if there is at least a 60% probability that the DLT rate is $< 30\%$,

$$\Pr(\pi_d < 30\%) > 60\%.$$

Patients cannot be assigned to a dose that is not safe by this definition.

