13.5.3 Dose Escalation Rules

Dose escalation begins with enrollment of patients on the 0.003 mg/kg dose. The queue refers to the number of patients that have been allocated to doses, but have not yet completed the observation period. For safety purposes we want to keep the queue size moderate to prevent large numbers of patients being enrolled at any one time. Until 4 patients have complete DLT information the queue maximum is 2. After 4 patients have complete DLT information, the queue increases to 3. Patients cannot be enrolled for dose escalation if the queue maximum has been reached.

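### No hematologic DLT in an ATLL patient can be scored before Day 42, but the CRM queue and the 2-patient escalation condition close that patient's DLT window at Day 21

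*Protocol*

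**What the plan says.** Protocol 7.3.1.1 (repeated in the synopsis) says that the usual hematologic DLTs do not apply to ATLL patients and gives two substitutes. Grade 4 neutropenia must last at least "42 days from the start of the cycle in the absence of evidence of residual leukemia". Grade 3 or higher thrombocytopenia, or Grade 4 anemia, must come with a hypocellular marrow, persist for the same 42 days, and occur without residual leukemia.

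The escalation machinery runs on a shorter clock:

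- Appendix 13.5.1: "The DLT observation period is 1 cycle". Section 6.1 sets a cycle at 21 days.
- Appendix 13.5.3: "The queue refers to the number of patients that have been allocated to doses, but have not yet completed the observation period". The queue maximum starts at 2. "After 4 patients have complete DLT information, the queue increases to 3".
- Appendix 13.5.3.2: "There must be complete DLT information through the first cycle (3 weeks) on at least 2 patients in order to escalate".
- The same section sets the step limits: "Once a non-DLT toxicity is observed, the dose may only be increased by 67" per cent, and "once a DLT is observed, the dose may only increase by 50" per cent.
- Appendix 13.5.2 calls a dose safe when the probability that its DLT rate is below 30% exceeds 60%, and adds: "Patients cannot be assigned to a dose that is not safe by this definition".

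Section 7.3.1.1 also states that the algorithm takes in cumulative DLTs through Cycle 3. Neither document gives ATLL patients a longer window or a pending status.

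**The concern.** Take an ATLL patient with an open Grade 4 neutropenia on Day 21. The earliest the event can become a DLT is Day 42. As written, the patient leaves the queue at Day 21 and becomes one of the two patients who permit escalation. A dose decision can therefore rest on a patient whose hematologic DLT status could not yet have been settled, whatever happened in the first cycle.

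The coding matters in two ways. A Grade 2 or higher toxicity limits the next step to 67%, and a DLT limits it to 50%. A DLT also lowers the model's highest safe dose. For about three weeks, the next patients could receive a dose that the same event would rule out once classified.

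**Working it through.** **Timing.** The plan's own window is 1 cycle = 3 × 7 = 21 days, which agrees across Sections 6.1 and 7.3.1.1 and Appendices 13.5.1 and 13.5.3.2. The earliest ATLL hematologic DLT is at Day 42, so the gap is 42 − 21 = 21 days. Cycle 3 nominally ends at 3 × 21 = Day 63, so a Day 42 event is still caught by the through-Cycle-3 rule. With the 7-day stagger between the first two patients at a new dose, both are complete on Day 7 + 21 = 28. The remaining gap is then 42 − 28 = 14 days if the first patient has the event, and (7 + 42) − 28 = 21 days if the second has it.

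**Dose grid.** The four ranges in Appendix 13.5.1 give 18 + 6 + 5 + 4 = 33 levels, as stated.

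**Step caps alone.** For current dose d in µg/kg, the maximum next dose is the highest level not above the smallest of d × 1.67 (or d × 1.50), d + 20 if d < 100 (otherwise d + 100), and 300. If the event would be the trial's first DLT, the two codings compare as follows over the 32 levels below 300:

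| Difference in maximum next dose (µg/kg) | Current dose levels (µg/kg) | Count |
|---|---|---|
| 1 | 3, 5, 6, 7, 8, 10, 13 | 7 |
| 2 | 9, 11, 12 | 3 |
| 5 | 15, 16, 18, 19, 25, 30 | 6 |
| 50 | 150 (250 vs 200) | 1 |
| 0 | 4, 14, 17, 20, 35 to 100, 200, 250 | 15 |

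The caps differ at 17 of 32 levels, and 16 of the 17 are at or below 30. At 45, the starting dose of every listed Part 2 regimen, the limits are 45 × 1.67 = 75.2, 45 × 1.50 = 67.5 and 45 + 20 = 65. The next level is 60 under either coding.

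**Caps and the 60% rule together.** The Appendix 13.5.2 model was integrated numerically with its stated priors and pseudo-observations, dose in mg/kg. The patient data are assumed: 2 toxicity-free patients at each of 3, 6, 12, 20, 40, 60, 80 and 100 µg/kg below the event level, then 1 of 2 with the event. Ranges reflect two readings of the pseudo-observations (DLT versus no DLT only, or the non-DLT share counted as no toxicity).

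| Event at (µg/kg) | Dose tested | Pr(DLT rate < 30%), scored Grade 2+ | Scored DLT | Decision changes? |
|---|---|---|---|---|
| 40 | 60 | 0.99 | 0.94 | No |
| 60 | 80 | 0.98 | 0.91 | No |
| 80 | 100 | 0.97 | 0.86 | No |
| 100 | 150 | 0.78–0.79 | 0.53–0.55 | Yes |
| 100, 3 per level, 1 of 3 affected | 150 | 0.83–0.84 | 0.62–0.64 | No |
| 100, 2 per level, 1 of 4 affected | 150 | 0.84–0.85 | 0.63–0.65 | No |
| 150 | 200 | 0.56–0.59 | 0.28–0.30 | No (blocked both ways) |

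The first three rows use the first reading only. The last row shows that, in these data, the 50 µg/kg cap difference at 150 is not realised. If one earlier DLT had occurred at 40, 60 or 80 µg/kg, then 150 is blocked under both codings (first reading: 0.58, 0.52, 0.46 against 0.38, 0.32, 0.26).

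**The case against.** The best defence is that the protocol has already chosen how to treat late events. One cycle gates escalation, and DLTs through Cycle 3 update the model. Completeness in Appendix 13.5.3.2 is expressly for the first three weeks; it is not a claim that DLT status is final. That reading is fair, and it rules out saying that ATLL hematologic DLTs are lost. It does not alter the queue or the 2-patient count at Day 21.

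A reader might infer that ATLL is the only case in which an event is visible but unclassified at Day 21. It is not. In other patients, a Grade 4 neutropenia that begins late in Cycle 1 cannot yet have lasted more than 7 days. The true difference is that non-ATLL hematologic DLTs are left open only when they start late, whereas every ATLL hematologic DLT is left open.

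A reader might also call any Day 21 cytopenia a probable DLT. The criteria further require no residual leukemia and, for platelets or hemoglobin, a hypocellular marrow. Section 4.2.1 waives the entry count limits for ATLL, so some patients may start cytopenic.

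The Dose Escalation Steering Committee can be more conservative than the model (Section 7.3.1.2), and an open Grade 4 cytopenia would be available for its review. That is a real safeguard, though a discretionary one. Section 6.4 allows a dose delay of up to 21 days, which might seem to extend the window, but Appendix 13.5.3.2 fixes it at 3 weeks.

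Finally, it is tempting to ask for a change to the SAP's DLT-evaluable set. The documents do not support the need. SAP 4.1.2 already includes a patient who completes the cycle, and the DLT table in SAP 4.8.1 has no Cycle 1 cut-off, so a Day 42 DLT can be tabulated as written.

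**Conclusion.** The mismatch is real and follows from the text alone: the escalation gate closes 21 days before any ATLL hematologic DLT can be scored. The consequence is delayed scoring for at most 2 to 3 queued patients, with the cytopenia already in the model as a Grade 2 or higher toxicity.

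The size is small. Cap differences need this to be the trial's first DLT. The single changed model decision, 100 to 150 µg/kg, depends on assumed data and disappears under other plausible data. The documents do not give the number of ATLL patients, so the overall effect cannot be estimated. A stronger reading, that the design exposes patients to materially excessive doses, is not supported. This is a minor point, worth correcting because the correction is cheap.

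**What to change.** Amend Appendix 13.5.3 only:

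- **Definition.** An ATLL patient is DLT-pending if, at Day 21, there is an unresolved Grade 4 neutropenia, Grade 3 or higher thrombocytopenia or Grade 4 anemia that is new or worse than baseline and not clearly due to disease.
- **Handling.** The patient stays in the queue and does not count toward the 2-patient condition until recovery, classification under the full Section 7.3.1.1 criteria, or Day 42, whichever is first.
- **Model.** The observed Grade 2 or higher toxicity, or any non-hematologic DLT, enters the CRM at once.
- **Unknown status.** If Day 42 status cannot be established, release the slot and keep the toxicity in the model, but do not count the patient toward the two. This can happen because adverse event assessment may end when new anticancer treatment starts (Section 7.3.2.2).

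The sponsor's clinical DLT definition stays as it is. The cost is a few sentences, with no new visit or procedure. One of the 2 to 3 queue slots may be held up to about 3 weeks longer for an affected patient. A baseline cytopenia that has not worsened holds no slot.
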